2.2 Secondary outcomes

Clinical outcomes

1. Serum haemoglobin levels.
2. Time to wean from ECMO.
3. Percentage of patients weaned from ECMO within 7 days
4. AKI as defined by the KDIGO pediatric definition (Table 1)
5. AKI as defined based on the neonatal modification (Table 2)
6. Heart injury as determined by serum troponin levels.
7. Renal inflammation as determined by urine NGAL concentrations.
8. Allogenic red cell transfusion volume.
9. Non red cell transfusion volume.
10. Time to discharge from Glenfield Hospital ICU.
11. Time to Glenfield Hospital discharge.
12. Measures of haemoglobin metabolism e.g. serum hepcidin, serum haptoglobin, transferrin saturation, serum ferritin, plasma labile iron concentrations.
13. Inflammatory cytokines in serum, measured by IL-6, IL-8, TNF α , MCP-1 and MIP-1.
14. Other adverse events not specified above.

Feasibility outcomes

15. Recruitment, sampling rates, and Withdrawal rates
16. Protocol adherence including clinical and laboratory protocol adherence
17. Data completeness
18. Experience of parents/ family/ guardians in relation to the screening, consent and study procedures based on a questionnaire

Table 1. Pediatric KDIGO-staging system for acute kidney injury, as per reference [1], with modified Stage 3 as per the pRIFLE definition [2].

Stage	Serum creatinine (SCr) criteria	Urine output criteria
1	SCr \geq 26 $\mu\text{mol/L}$ increase or SCr \geq 1.5- to 2-fold from baseline	<0.5 ml/kg/hr for > 6 consecutive hrs
2	SCr \geq 2 to 3-fold from baseline	<0.5 ml/kg/hr for > 12 hr
3	SCr \geq 3-fold from baseline or SCr \geq 354 $\mu\text{mol/L}$ or Renal replacement therapy irrespective of stage or *Decrease in estimated Creatinine Clearance (eCrCl) to less than 35 mL/min/1.73 m ² using the Schwartz equation: eCrCl(mL/min/1.73 m ²) = (36.2 \times Height in cm) / Creatinine in $\mu\text{mol/L}$	<0.3 ml/kg/hr for > 24 hr or anuria for 12 hr

The above criteria include both an absolute and a relative change in creatinine to accommodate variations related to age, gender, and body mass index and to reduce the need for a baseline creatinine but do require at least two creatinine values within 48 hours. Only one criterion (creatinine or urine output) has to be fulfilled to qualify for a stage. 200% to 300% increase = 2- to 3-fold increase. Given wide variation in indications and timing of initiation of renal replacement therapy (RRT), individuals who receive RRT are considered to have met the criteria for stage 3 irrespective of the stage they are in at the time of RRT. The modified stage 3 criteria for children* reflect the observation that infants with small body mass may be unable to generate high serum creatinine values.

Table 2. Neonatal acute kidney injury definition – modification from KDIGO pediatric AKI definition [3].

Stage	Serum creatinine (SCr) criteria Neonatal modification: 2015-2016	Urine output criteria Neonatal modification 2016
1	SCr \geq 26 $\mu\text{mol/L}$ increase or SCr \geq 1.5- to 2-fold from baseline	\leq 1 ml/kg/hr for 24 hr
2	SCr \geq 2 to 3-fold from baseline	\leq 0.5 ml/kg/hr for 24 hr
3	SCr \geq 3-fold from baseline or SCr \geq 221 $\mu\text{mol/L}$ or Renal replacement therapy irrespective of stage	\leq 0.3 ml/kg/hr for 24 hr

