1.1 Aims and Objectives

Hypothesis

The primary hypothesis is that damage to red blood cells by the exposure to the ECMO circuit will result in inflammatory responses that mitigate against successful weaning from ECMO for PPHN.

The secondary hypothesis are:

1. Damage to red cells will result in platelet, leukocyte and endothelial activation.
2. Markers of platelet, endothelial and leukocyte activation are indicators of lung inflammation and injury severity and hence lung recovery.
3. Markers of platelet, endothelial and leukocyte activation are indicators of kidney injury severity and hence acute kidney injury.
4. Granulocyte and platelets activation are secondary to rising redox potential and the levels of activation will correlate with longer intubation times and more severe organ injury.
5. Markers of platelet, endothelial and leukocyte activation have diagnostic and prognostic utility for the prediction of key clinical events including delayed time to recovery, acute kidney injury in paediatric patients undergoing ECMO for PPHN.

Objectives

The Mi-ECMO study was designed to be a feasibility study, and the results will be used to assist with the design of a prospective observational study that will test the above hypotheses. The objectives of the study are:

1. To determine the recruitment rates and patient flows for 24 patients recruited for the feasibility study.
2. To determine the withdrawal rate and the completeness of follow-up and data collection in a paediatric population at high risk for death and major morbidity.
3. To collect data on primary and secondary outcomes of interest, which may be used to model the sample sizes and outcomes in future study.
4. To collect data on perception of family members, whose children participate in the study, as to their understanding of the screening and consent process (Appendix 1).

Changes in hypothesis

Due to the lack of ethical approval, this study is not conducting analysis of bronchial aspirates, and measuring markers of oxidative stress and MV levels. The following secondary hypothesis which were stated in the study protocol have not been included in this SAP:

1. The level of oxidative stress will correlate with type shifts in pulmonary macrophages, tissue iron deposition and organ injury.
2. Ability to raise anti-oxidative response, measured by Heme Oxygenase-1 (HMOX 1) expression, will correlate with shorter intubation times and less severe kidney and lung injury.

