2.3 Target conditions

1. Prolonged ECMO defined as patients remained on ECMO at day 7 (duration of ECMO >168 hours)
2. AKI as defined by the KDIGO stage 1, 2 or 3 using the paediatric AKI definition (Table 1).
3. AKI as defined by the KDIGO stage 1, 2 or 3 using the serum creatinine criteria for the neonatal AKI definition (Table 2).

3. Analysis Sets/Populations

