4.3 Descriptive Analysis

Descriptive analysis will be presented for demographic and baseline characteristics, as well as the primary and secondary outcomes, and targeted conditions described in Section 2. For categorical variables, numbers and percentages will be presented. For continuous variables, mean and standard deviation or median with lower and upper quartiles, as appropriate, will be presented.

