4.5 Subgroup analysis

Exploratory analysis may be carried out to assess the relationship of cellular activation with the targeted subgroups:

- Patients on ECMO within 7 days vs 7+ days
- Patients with and without AKI

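### The eCrCl limb of SAP Table 1 can classify an infant as Stage 3 AKI before either Stage 1 creatinine criterion is met, and no planned analysis isolates the cases it alone creates

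*SAP*

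**What the plan says.** SAP 2.2, Table 1, gives Stage 3 several alternative routes. One is "Decrease in estimated Creatinine Clearance (eCrCl) to less than 35 mL/min/1.73" mL/min/1.73 m², computed as 36.2 × height (cm) / creatinine (µmol/L). Stage 1 by creatinine needs a rise of at least 26 µmol/L or at least 1.5 times baseline. The note below the table adds that "Only one criterion (creatinine or urine output) has to be fulfilled to qualify for a stage", and that the criteria "do require at least two creatinine values within 48 hours". It attaches no minimum change to the eCrCl limb. The note justifies the limb on the ground that small infants may not generate high creatinine.

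The limb comes from the protocol: it is in Table 1 of section 5.3.2, and section 6.5 confirms that estimated clearance is used for Stage 3.

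SAP 2.3 sets two AKI target conditions:
- Condition 2: "AKI as defined by the KDIGO stage 1, 2 or 3 using the paediatric AKI definition (Table 1").
- Condition 3: "AKI as defined by the KDIGO stage 1, 2 or 3 using the serum creatinine criteria for the neonatal AKI definition (Table 2").

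SAP 4.3 reports descriptively the "targeted conditions described in Section 2", so both are covered. SAP 4.5 allows an exploratory comparison of "Patients with and without AKI" without naming the definition. Objective 3 in SAP 1.1 is to collect outcome data "which may be used to model the sample sizes and outcomes in future study".

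**The concern.** Stages are meant to be ordered: Stage 3 should reflect a larger change than Stage 1. Here a fixed clearance limit stands beside relative creatinine criteria. In a newborn, whose length is small, that limit corresponds to a low creatinine. A small rise across it is then graded as the most severe stage, while a larger rise below it is graded as the mildest.

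Because condition 2 counts any stage as AKI, the ordering problem also reaches the yes/no outcome. At stake are the AKI proportion and stage distribution carried into the next study, and the make-up of the AKI groups if the comparison in SAP 4.5 is run. With 24 infants, each reclassification moves the proportion by 1/24 = 4.2 percentage points.

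**Working it through.** The documents state no AKI figure derived from this definition, so there is nothing to reproduce. The check is algebra on the SAP's formulas. Lengths and creatinine values are assumptions, because the documents give none.

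**Creatinine at which the limb is met.** eCrCl < 35 means creatinine > c, where c = 36.2 × L / 35.
- L = 45 cm: 1629/35 = 46.5 µmol/L
- L = 50 cm: 1810/35 = 51.7 µmol/L
- L = 55 cm: 1991/35 = 56.9 µmol/L

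**Stage 1 by creatinine.** With reference value B, Stage 1 is reached at the smaller of B + 26 and 1.5 × B. Below B = 52 the 1.5-fold rule comes first.

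**Where Stage 3 comes first.** This needs B ≤ c and c below the Stage 1 value, which gives B between c/1.5 and c.
- 45 cm: 31.0 to 46.5
- 50 cm: 34.5 to 51.7
- 55 cm: 37.9 to 56.9

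This equals a reference eCrCl from 35 up to 35 × 1.5 = 52.5. At lower reference creatinine, Stage 1 comes first or at the same point.

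**Examples at 50 cm, creatinine criteria only.**

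| Creatinine | Change | eCrCl | With limb | Without limb |
|---|---|---|---|---|
| 40 to 52 | +12, 1.30-fold | 45.3 to 34.8 | Stage 3 | none |
| 50 to 52 | +2, 1.04-fold | 36.2 to 34.8 | Stage 3 | none |
| 30 to 50 | +20, 1.67-fold | 60.3 to 36.2 | Stage 1 | Stage 1 |

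From references of 40, 45 and 50, the limb is reached after rises of 11.7, 6.7 and 1.7 µmol/L. Stage 1 needs rises of 20, 22.5 and 25.

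**Other fixed limits.** These behave the same way but over narrower relative bands: Table 2's 221 limit for references 195 to 221 (ratio 1.13), and Table 1's 354 limit for 328 to 354 (ratio 1.08). The eCrCl band has ratio 1.50.

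**Does condition 3 isolate the limb?** No. Condition 3 drops the limb, drops urine output, and replaces the 354 limit with 221. Secondary outcome 5 applies Table 2, but its urine thresholds differ from those in Table 1. Neither contrast changes only the limb.

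**Infants already below 35 at reference.** At 50 cm, 55 to 75 µmol/L (+20, 1.36-fold; eCrCl 32.9 to 24.1) is no AKI by creatinine if 35 must be crossed. It is Stage 3 if any further fall counts. The SAP does not say which applies.

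**Which value is the reference?** The SAP 1.5 schedule labels the 12 h visit as baseline, and the protocol 6.5 creatinine series starts there. The SAP Appendix also lists a pre-ECMO creatinine. Take 30 pre-ECMO and 60 at 12 h and 24 h, at 50 cm, with all values inside the 48-hour window. The pre-ECMO reference gives Stage 3 (Stage 2 without the limb). The 12 h reference gives no AKI by creatinine, because nothing falls after it.

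**Illustration of measurement noise.** This assumes a constant true creatinine, 50 cm, one reference and four later values, CV 5%, and the limb coded as a crossing. The limb fires in about 0.6%, 21% and 51% of infants at true values of 45, 48 and 50, and a Stage 1 creatinine criterion in 0%. At a true value of 40 it fires in 0%, and in about 0.7% even at CV 10%. If only the 24 h and 48 h values count, the figures at 48 and 50 fall to about 11% and 32%. The effect is confined to values just under the cut-off.

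**The case against.** The strongest reply is that the SAP applies an adopted definition as the protocol specifies it, with a stated reason, and that any fixed limit beside relative stages produces such a band. The first part stands: a reader might infer that the limb is a mistake or that 35 is the wrong threshold for newborns, and the documents do not support that. But the stated reason explains why the limb exists. It does not address the ordering against Stage 1, and the other fixed limits give narrower relative bands.

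A second reply is that a definition without the limb is already prespecified and reported, and that SAP 4.5 is exploratory and optional. Both are true. Since both AKI definitions are target conditions, running 4.5 under each is a natural reading. Yet neither shows how many condition 2 cases rest on the limb alone.

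Three stronger inferences also fail:
- **A count of affected infants.** One could take the 64% AKI frequency in protocol 3.2 and treat the remaining 36% of 24, about 9, as a ceiling. That frequency is cited from another study without its AKI definition, so it does not bound this cohort.
- **A level reading.** Counting an unchanged eCrCl below 35 as Stage 3 conflicts with the SAP's wording, which requires a decrease. Only crossing and further fall remain open.
- **Crossing as the correct rule.** No passage favours it, and the noise illustration already uses it, so choosing it would not remove sensitivity near the cut-off.

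**Conclusion.** The concern holds in a limited form. The ordering follows directly from the SAP's equation and stage criteria: for reference creatinine between two-thirds of the cut-off and the cut-off, Table 1 gives Stage 3, and so AKI under condition 2, before either Stage 1 creatinine criterion. The band in µmol/L depends on assumed length; its 1.5-fold width does not over 45 to 55 cm.

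The yes/no outcome changes only for infants not already AKI by urine output or renal replacement therapy, and only where the two-value condition is met. The number among the 24 cannot be derived or usefully bounded. The noise figures are illustrative and should not be read as a false-positive rate for the cohort. Priority is minor to moderate, because AKI is a secondary, descriptive outcome in a feasibility study. Whether 35 is the right clinical threshold is not judged here.

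**What to change.** Main change:
1. Keep the Table 1 outcome. Report its AKI proportion and stage with and without the eCrCl limb, and count infants who are AKI by that limb alone (no other creatinine, urine output or renal replacement criterion met).
2. If the exploratory AKI comparison in SAP 4.5 is run, run it under conditions 2 and 3, and for condition 2 also without the limb.

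Secondary clarifications, to be settled before analysis:
- State how an infant already below 35 at reference is classified (crossing required, or any further fall), and count such infants. Either choice can be defended; what matters is that it is stated.
- Reconcile the 12 h baseline with the listed pre-ECMO creatinine, and name the reference used for staging. This affects every fold-change criterion in both tables.
- Add body length to the SAP Appendix. The equation needs it and the list gives only weight. Its absence from the list does not show that it was not collected.

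The cost is a few sentences in the SAP and a few extra tabulations in 24 infants, plus extraction of length if it is not already in the dataset. No protocol outcome is removed or redefined.

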2.3 Target conditions

1. Prolonged ECMO defined as patients remained on ECMO at day 7 (duration of ECMO >168 hours)
2. AKI as defined by the KDIGO stage 1, 2 or 3 using the paediatric AKI definition (Table 1).
3. AKI as defined by the KDIGO stage 1, 2 or 3 using the serum creatinine criteria for the neonatal AKI definition (Table 2).

3. Analysis Sets/Populations

3.1 Full analysis set population

The full analysis set population comprises all recruited patients with full consent. This population comprises 24 patients. All analyses of clinical outcomes will be carried out on the full analysis set population.

3.2 Safety population

The safety population comprises all recruited patients with either emergency consent or full consent even those withdrew from the study. This population will be used for safety analyses.

3.3 Protocol deviations

Potential deviations from the protocol and their categorisation into major/minor are to be discussed by the trial team. In general, protocol deviations would be considered as major if they could potentially lead to biased estimations of primary or secondary endpoints (e.g. entered into the study in error). Time window violations are generally not considered as major protocol deviations.

4. Statistical Methodology

4.1 Timing of Analysis and Interim Analysis

Analysis are to be performed when the final dataset with all laboratory data are ready. No interim analyse have been planned before the end of the recruitment phase.

4.2 Disposition of Patients

Patient disposition will be presented with respect to recruitment rates, withdrawal rates, as well as protocol adherence including clinical and laboratory protocol adherence.

Data completeness will also be summarized.

4.3 Descriptive Analysis

Descriptive analysis will be presented for demographic and baseline characteristics, as well as the primary and secondary outcomes, and targeted conditions described in Section 2. For categorical variables, numbers and percentages will be presented. For continuous variables, mean and standard deviation or median with lower and upper quartiles, as appropriate, will be presented.

4.4 Statistical Methods

Mixed effects model with patient as random effect will be used to analyse outcomes measured at multiple time points. Logarithm transformation will be considered for skewed variables. Linear graphs showing the variation of the mean measurements over time will be displayed.

Exploratory analysis are to be carried out using mixed effects models to examine serial makers of cellular activation and their relationship with:

- Duration on ECMO

- Transfusion volume
- Free cell haemoglobins
- NGAL concentrations
- Serum troponin levels
- Inflammatory cytokines

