5.4.8 Administration of non-RBC Blood Components

Children receiving blood transfusions frequently receive non RBC components that can affect inflammatory responses. These will be administered according to standard unit protocols, with the indication, volume and timing of their administration recorded.

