Total iron and non-transferrin-bound iron (NTBI) levels will be measured as previously described (Gosriwatana et al., 1999). Iron is detected by measuring absorbance at 525 nm in colorimetric reaction with bathophenanthroline disulfonic acid disodium salt hydrate (BPT). For NTBI samples will be treated with iron chelator (nitrilotriacetic acid, NTA), ultrafiltered and analysed with BPT.

Oxidative stress will be measured in plasma using commercially available carbonylation kit (R&D Systems, Minneapolis MN).

HMOX-1, iNOS and Arg-1 expression will be estimated in cells from bronchial aspirates by Western blotting with specific antibodies.

Platelets and leukocyte activation, as well as platelets—leukocyte aggregates will be determined with specific antibodies (CD41, PAC-1 and CD62P for platelets, CD64, CD163 and CD11a for leukocytes and CD14, CD16, CD41 for the aggregates) and analysed by flow cytometry. Full blood count will be measured.

Urine biomarkers of renal oxidative stress; NGAL (ELISA Biporto Diagnostics A/S Denmark) and/will be measured on the DS2 automated ELISA platform (Dynex, through Alere, UK).

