7.1 Sample Size

This is a feasibility study and no formal power calculation has been performed. Our sample size is based on our observations from the 24 patients in the p-MiVAKI study (63), where we have demonstrated significant differences in markers of platelet, leukocyte and endothelial activation between patients who subsequently did or did not develop AKI, and between those that did or did not receive transfusion.

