1.3 Sample Size

The Mi-ECMO study enrolled 24 patients. There was not a formal power calculation for this feasibility study. The sample size was based on the observations from a similar study, p-MiVAKI which had recruited 24 paediatric patients and was able to demonstrate differences in the primary outcomes, markers of platelets, leukocyte and endothelial activation, between those who did and did not develop AKI, and between those did and did not receive transfusion.

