2.1 Primary outcomes

Markers of cellular activation including platelet, leukocyte and endothelial cell activation in arterial blood at baseline (12 hours after ECMO commencement) and then at 24, 48 and 72 hours post commencement and at weaning (24 hours after decannulation) or immediately prior to ECMO support being stopped in case of death or treatment withdrawal.

Markers of cellular activation include CD41, PAC-1 and CD62P for platelets, CD64 and CD163 for leukocytes, CD14, CD16, and CD41 for platelet-leukocyte aggregates, as well as circulating ICAM and E-selectin for endothelial injury.

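### Cheap improvement: SAP 4.4 should split transfusion volume by product and by sampling interval, because platelet markers in samples taken after a platelet transfusion may partly measure donor platelets

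*SAP*

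**What the plan says.** The primary outcome in SAP 2.1 is a set of serial markers: "Markers of cellular activation include CD41, PAC-1 and CD62P for platelets", plus leukocyte markers, platelet-leukocyte aggregates (CD14, CD16, CD41), and ICAM and E-selectin for the endothelium. Protocol 6.5 says the platelet, leukocyte and aggregate markers are "analysed by flow cytometry". It describes no step that tells donor platelets from the infant's own.

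SAP 4.4 states the main model: "Mixed effects model with patient as random effect will be used to analyse outcomes measured at multiple time points". It then lists exploratory relationships of the markers with ECMO duration, "Transfusion volume", free haemoglobin, NGAL, troponin and cytokines. The transfusion item has no product, interval or lag. The SAP does not say whether the listed items enter together or one at a time. No transfusion term is named for the main serial model or for the AKI and 7-day comparisons in SAP 4.5.

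Protocol 5.4.8 recognises the issue: "Children receiving blood transfusions frequently receive non RBC components that can affect inflammatory responses". It says these products are given under unit protocols, "with the indication, volume and timing of their administration recorded".

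Elsewhere the SAP does distinguish products. Outcomes 8 and 9 in SAP 2.2 are red-cell and non-red-cell volumes. The SAP Appendix has separate yes/no items for each, reported before, during and after ECMO.

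**The concern.** CD41, PAC-1 and CD62P identify platelets and their activation state, not whose platelets they are. If an infant receives platelets between two samples, the second sample may contain donor cells. Any difference in their activation then appears as a change over time in the infant.

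Transfusion is also likely to track the quantities that SAP 4.4 and 4.5 relate to the markers, such as long runs, haemolysis and AKI. A transfused product then competes with circuit damage as the explanation for the same signal. The study team's previous paediatric study found that these markers differed by transfusion status, and Protocol 7.1 uses that result to support the sample size. It is not carried into the models as an adjustment.

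What is at stake is attribution. The primary hypothesis concerns red-cell damage from the circuit, and the third study objective uses these outcomes to model the definitive study. Unmodelled donor platelets could affect both the mean trajectories and the variances carried forward.

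**Working it through.** The plan has no figure to reproduce: the sample of 24 has no alpha, power, effect size or SD behind it. The check sets the texts side by side and then asks whether the form of the transfusion term matters.

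**Texts.** The Protocol records volume and timing of non-red-cell products. The SAP models use neither product nor timing. The Appendix periods (before, during, after ECMO) cannot assign a transfusion to the 12, 24, 48 or 72 h sample.

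**Mixture arithmetic.** Let f be the donor share of platelets in the tube. Observed % activated = (1 − f) × own + f × donor. Own activation is assumed to be 10%.

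| Donor activation | f = 0.10 | f = 0.25 | f = 0.50 |
|---|---|---|---|
| 10% | 10.0 | 10.0 | 10.0 |
| 20% | 11.0 | 12.5 | 15.0 |
| 30% | 12.0 | 15.0 | 20.0 |
| 40% | 13.0 | 17.5 | 25.0 |

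**Simulation.** It used 24 patients, five samples each, a random patient intercept, no true ECMO effect and 200 runs per scenario. All of the following are assumptions, not document figures:
- own activation mean 10%, between-patient SD 3, residual SD 2
- donor share 15% to 45% (mean 30%) in a sample after transfusion
- probability of transfusion before the five samples 0.2, 0.5, 0.5, 0.4, 0.1

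The expected false rise at 24 to 72 h over the 12 h sample can be written down. The mean on-ECMO probability is (0.5 + 0.5 + 0.4)/3 = 0.467. Its excess over 12 h is 0.467 − 0.2 = 0.267, and times 0.30 this is 0.080. Multiplying by the activation gap gives 0.080 × 10 = 0.8, 0.080 × 20 = 1.6 and 0.080 × 30 = 2.4 points. The simulation agrees. Each cell shows the false rise in points and the share of runs with nominal p < 0.05:

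| Donor activation | No transfusion term | One total per patient | Sample-timed platelet term |
|---|---|---|---|
| 10% | 0.01; 7.5% | 0.01; 7.5% | 0.02; 7% |
| 20% | 0.80; 27% | 0.80; 27% | 0.01; 3% |
| 30% | 1.58; 48.5% | 1.58; 48.5% | −0.01; 7% |
| 40% | 2.45; 59.5% | 2.45; 59.5% | 0.02; 7% |

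A per-patient total is constant within a patient, so with all five samples present it cannot alter a within-patient time contrast. Only a term that varies by sample can.

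**Limits.** The timed term here was the donor share itself, which is a best case; recorded volume is a cruder proxy and would remove less. The false rise also depends on transfusion being more likely before the 24 to 72 h samples than before the 12 h sample. With equal probabilities this contrast would show none.

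**The case against.** Several objections have force.

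- **Platelet transfusion is never named.** A reader might infer that the primary markers are in fact read on a donor/own mixture. The documents do not support that: they speak only of non-red-cell products and give no frequency. Only a possibility can be claimed.
- **The SAP does separate products.** A reader might infer that it pools them or ignores timing throughout. It does not: outcomes 8 and 9 and the Appendix items distinguish red-cell from non-red-cell products, and the term in 4.4 may be shorthand for both. The gap is in the 4.4 models, where the term is undefined, platelets are not isolated and nothing is tied to a sample.
- **The size might be inferred from donor share.** Assume a blood volume of 85 ml/kg, 10 to 15 ml/kg of product at 800 to 1200 ×10⁹/L, 70% recovery and an own count of 50 to 150 ×10⁹/L. The share just after transfusion then runs from 5600/(5600 + 12750) = 0.31 to 12600/(12600 + 4250) = 0.75. Every input comes from outside the documents. The figure ignores the delay to the next sample (scheduled on-ECMO samples are 12 to 24 h apart) and says nothing about activation. It is not a bias estimate.
- **The hypotheses are not confined to the infant's own cells.** They refer to platelet, leukocyte and endothelial activation, and the rationale includes donor blood in the circuit. This stands, but separating circuit effects from transfused product still matters for interpretation. Donor-platelet carry-over does not concern CD64, CD163, ICAM or E-selectin.
- **Adjustment can mislead.** Platelets may be given because of activation or bleeding, so conditioning on them can remove part of the effect, and dropping samples may select less ill infants. This stands and shapes the fix.
- **The stakes are modest.** The Protocol says "This is a feasibility study and no formal power calculation has been performed", the marker relationships are exploratory, and the SAP introduction already permits unplanned analyses. This limits the severity. It does not remove the point, because the estimates feed the next study and a prespecified check is worth more than one chosen after seeing the data.

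**Conclusion.** The point holds as a cheap improvement. The SAP 4.4 models do not use product or timing information that the Protocol says is recorded and itself links to inflammatory responses. Platelet markers and platelet-leukocyte aggregates may therefore carry a transfusion signal that is read as ECMO-related activation.

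The size is unknown. It depends on how often platelets are given, how close to sampling, and how donor activation compares with own, none of which the documents state. The simulated 0.80 to 2.45 points shows only that a per-patient total cannot remove a transfusion effect that varies between samples, and that a sample-timed term can. The plan is not shown to be biased.

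**What to change.** In SAP 4.4, replace the single transfusion item with separate red-cell and non-red-cell volumes (outcomes 8 and 9), and split platelets from other products where the records allow. Total each over the interval before each sample, using actual collection times because the sampling windows are wide. For the 12 h sample, count from the earliest recorded transfusion, including any before ECMO.

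For platelet markers and platelet-leukocyte aggregates only, keep the planned models as the main analysis and add two sensitivity analyses:
- (a) include the sample-timed platelet-transfusion term
- (b) exclude samples taken after a platelet transfusion in the preceding interval

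State the downsides in the SAP: fewer samples, possible selection of less ill infants, and possible removal of part of the effect if transfusion follows from activation or bleeding. These are the reasons for not making either the main analysis.

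The cost is SAP wording and a few derived variables, with no new sampling and no change to care. Two things need confirming on the case report form: that platelets are identifiable within non-red-cell products, and that red-cell times are held, since the timing statement in Protocol 5.4.8 covers only non-red-cell products.
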